2.0 STUDY OBJECTIVES

The purpose is to prospectively study the feasibility to optimize configuration of CRT delivery for acute correction of electrical dyssynchrony using a noninvasive mapping of global electrical activation.

Study Hypothesis

Tailor-made configuration of CRT delivery is feasible and able to improve responder rate compare to single method of CRT delivery in candidates with known poor response to CRT.

Primary outcome measure

Responder rate of greater than 10% of LV end systolic volume reduction in patients undergoing tailor-made approach of CRT delivery at 6 months. The responder rate is to compare with pre-defined level of 40% for single method of CRT delivery namely biventricular pacing with LV lead in coronary sinus.

Secondary outcome measures

1. The acute electrical dyssynchrony indices of different methods of CRT delivery.
2. The hemodynamic responses of different methods of CRT delivery.
3. Procedure duration and implantation success rate of the optimal CRT delivery method as determined by the best improvement in electrical dyssynchrony indices.
4. Cine images (PA, LAO 30°, RAO 30°) and Chest X ray (PA view)
5. Peri-operative and 6 months follow-up complications rate:
 - a. Thromboembolic event
 - b. Dislodgement and migration of pacing leads
 - c. Phrenic nerve stimulation
 - d. Others
6. Echocardiogram parameters at baseline and 6 months: left ventricular systolic and diastolic volume, left ventricular ejection fraction, degree of mitral regurgitation, strain imaging.
7. NYHA class, 6 minute hall walk test and quality of life using Minnesota's questionnaire at baseline and 6 months.
8. Electrical parameters including threshold, sensitivity and lead impedance of pacing leads at implant and 6 months follow-up.

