5.0 STATISTICAL CONSIDERATION

Hypothesis

The null and alternative hypotheses are as follows:

H0: The responder rate of tailor-made approach \leq 40%

HA: The responder rate of tailor-made approach $>$ 40%

Sample size was calculated employing binomial methods with the following assumptions were used:

Expected responder rate for tailor-made approach =60%

Historical control responder rate =40%

Test significance level (a) = 0.05 (1-sided)

Power= 80%

Based on the above assumptions, the sample size was calculated as 77. Accounting for the attrition of 20%, the total required sample size is 93 patients with device implanted.

Statistical method for additional analysis

All continuous data will be summarized with the number of non-missing data, mean \pm standard deviation, median and range (minimum – maximum). T test will be used for the comparison between the groups. In case the assumption for t test is violated, then the equivalent nonparametric test, such as Wilcoxon rank sum test, Kolmogorov-smirnov test, will be used instead. The normality assumption will be tested by the normality test with the aid of QQ plot.

All categorical data will be tabulated with number of occurrence and percentage. Chi-square test will be used for the comparison between the groups. In case the expected counts in each cell is less than 5, then Fisher's exact test will be used instead.

Procedures for reporting any deviation(s) from the original statistical plan

Any deviations from the statistical analysis plan will be documented.

The treatment of missing, unused or spurious data, including drop-outs and withdrawals.

No imputation techniques will be used.

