6.0 PROTOCOL DESCRIPTION

Patient informed consent

The investigator is responsible for obtaining informed consent from each prospective study patient prior to the performance of any study related procedures. After a patient has been provided with the information of the study and given time to think on whether to participating into the study, the patient will be asked to sign and date a consent form. One copy of the signed patient consent form must be handed out to the patient and one must be filed by the investigator in the investigator files. After the patient and the investigator have signed and dated the consent form, the study data collection process may start.

Patients meeting all the inclusion criteria and not meeting any of the exclusion criteria are eligible for the study. Data will be collected at the following study visits:

Enrollment

Noninvasive electrical activation and acute hemodynamic study

Implant

[figure not shown]
Pre-discharge (PDH) (\leq 72 hours post implant)

Month 3 follow-up visit: 90 ± 14 days post implant

Month 6 follow-up visit: 180 ± 14 days post implant

Table 1. Data collection for each scheduled visit

	Enrollment	Implant *	PDH*	Month 3	Month 6
Patient Informed Consent	x				
Echocardiogram	x		x	x	x
Medical History	x				
Cardiovascular Medication	x	x	x	x	x
NYHA Class	x			x	x
6MHW	x			x	x
SF-36QoL	x			x	x
12-lead electrocardiogram	x	x		x	x
Cine images		x			
Device Interrogation		x	x	x	x
Adverse Event	x	x	x	x	x
Protocol Deviation	x	x	x	x	x

Figure 1. Study Flow Chart

Noninvasive mapping of electrical activation

Ventricular activation maps will be acquired simultaneously with hemodynamic measurements using noninvasive mapping system (ECVUE, Medtronic Inc, USA). A thoracic computed tomographic scan will be acquired with the electrodes attached to the patient. Local ventricular activation times will be defined as the onset of the QRS complex or the pacing spike to the maximal negative slope of each unipolar electrogram.

The following electrical dyssynchrony indices will be derived

- i) Total activation time (TAT) is defined as the time difference between the earliest and latest site of activation on the entire ventricular epicardium (LV and RV);
- ii) RVTAT is defined as the time difference between the earliest and latest site of activation on the RV ventricular epicardium;
- iii) LVTAT is defined as the time difference between the earliest and latest site of activation on the LV ventricular epicardium;

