Safety surveillance and reporting will be done for all patients enrolled in the study. This will be started from the time patient provides with the informed consent until the last study visit has been performed or the patient has died or the patient concludes his participation into the study.

All **Serious Adverse Event** is to be documented and reported to the research ethics committee within 24 hours of notification.

As soon as the final details are available for the AE, the information should be reported on the AE case report form:

- Hospitalization details (if applicable)
- Diagnostic test information (if applicable)
- Treatment given (if applicable)
- Final medical diagnosis and cause
- Patient condition
- Final AE status
- Seriousness of AE based on final medical diagnosis and cause
- Relationship of AE to clinical investigation based on final medical diagnosis and cause

Study Termination

All reasonable efforts should be made to retain the patient in the clinical investigation until completion of the clinical investigation.

If a patient concludes their participation in the study, the future care and management will not be affected, whether it is voluntary or otherwise:

- A patient completes the study (Month 6 follow-up).
- A patient / family member may request to withdraw from the clinical investigation at any time with no effect to the patient's present care.
- A patient dies.
- An investigator may withdraw a patient from the study at any time as according to the best interest to the patient.

Risks associated with Participation in the Clinical Investigation

The risks involved with this study are comparable to those associated with the implant of any CRT.

The additional risks are related to the computerized tomography of the heart with possible complication of contrast injury to kidney and allergic reaction. Other additional risks are related to pre-implantation electrical activation study which involves putting in pacing catheters and pressure monitoring catheters in the body with possible risk of injury to the heart, blood vessel, bleeding, wound complications and infection.

Risk Minimization Actions

Additional risks may exist. Risks can be minimized through compliance with this CIP, performing procedures in the appropriate hospital environment, adherence to subject selection criteria, close monitoring of the subject's physiologic status during research procedures and/or follow-ups.

Anticipated Benefits

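### Withdrawal from the study ends safety surveillance and leaves no provision for a month 6 echo, so later complications and still obtainable LVESV readings are lost

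*Combined protocol and SAP*

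**What the plan says.** All places are in the combined protocol and SAP.

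- **Study Termination (6.0)** lists four ways in which participation ends: completing month 6, withdrawal by the patient or family, death, and investigator withdrawal. On the last: "An investigator may withdraw a patient from the study at any time as according to the best interest to the patient". The same section asks for retention: "All reasonable efforts should be made to retain the patient in the clinical investigation until completion of the clinical investigation".
- **Adverse Events Recording and Reporting (6.0)** runs safety surveillance from consent "until the last study visit has been performed or the patient has died or the patient concludes his participation into the study".
- **Secondary outcome 5 (2.0)** is the "Peri-operative and 6 months follow-up complications rate", which covers thromboembolism, lead dislodgement, phrenic nerve stimulation and other events.
- **Primary outcome (2.0)**: "Responder rate of greater than 10% of LV end systolic volume reduction in patients undergoing tailor-made approach of CRT delivery at 6 months". The reading belongs to a scheduled visit (6.0): "Month 6 follow-up visit: 180 ± 14 days post implant".
- **Statistical Consideration (5.0)** deals with drop-outs and withdrawals in one sentence: "No imputation techniques will be used". It defines no analysis set.

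**The concern.** The protocol treats the end of participation as the end of data collection. For safety this is a written rule, since surveillance stops when the patient leaves. For the echo it is an omission, since no visit, echo or record review is scheduled after withdrawal.

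Two results are exposed. The complication rate is meant to cover 6 months but loses whatever happens between withdrawal and day 180. The responder rate needs a month 6 volume, and a patient withdrawn earlier has none, even if that patient would agree to one more echo.

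The only stated criterion for investigator withdrawal is the patient's best interest. The study is non-randomized and describes no masking, so the decision is made with the treatment and the clinical course in view. If patients who do badly are withdrawn more often, both results look better than the strategy performs. This point is about what is collected. How a missing reading is counted is a further question.

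**Working it through.** **The plan's own figures.** Section 5.0 gives 77 patients, raised for 20% attrition to 93 implanted. 77 × 1.2 = 92.4, rounded up to 93. The 77 reproduces as the per-group size of a two-sample comparison of 40% with 60% (one-sided 0.05, power 80%). The allowance therefore leaves room for 93 − 77 = 16 patients (17.2%) without a reading. The plan does not divide these between investigator withdrawal, patient withdrawal, death and missed visits.

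**What the text keeps and loses for a patient withdrawn before month 6**

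| Item | Before withdrawal | After withdrawal |
|---|---|---|
| Adverse events | Collected from consent and at every visit in Table 1 | Surveillance has ended |
| Month 6 LVESV | Not yet due | No provision |
| Recovery in the analysis | – | None; imputation is excluded |

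**Illustration for the responder rate.** From section 5.0: null rate 40%, one-sided level 0.05, 93 implanted. Assumed: only patients with a reading are analysed, all *k* withdrawn patients are non-responders, and the true rate is exactly 40%, so 0.40 × 93 = 37.2 responders are expected.

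- Patients with a reading: n = 93 − k.
- Expected observed rate: 37.2 / n.
- Cutoff: the smallest r with P(X ≥ r | n, 0.40) ≤ 0.05.
- False success chance: P(X ≥ r | n, 37.2/n), exact binomial.

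| k | n | Observed rate | Cutoff | False success |
|---|---|---|---|---|
| 0 | 93 | 40.0% | 46 | 0.040 |
| 2 | 91 | 40.9% | 45 | 0.061 |
| 3 | 90 | 41.3% | 45 | 0.060 |
| 5 | 88 | 42.3% | 44 | 0.088 |
| 9 | 84 | 44.3% | 42 | 0.172 |

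The rows for 2 and 3 barely differ because the cutoff is a whole number. All these values of k are below 16.

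**Sensitivity to the split.** If the number lost varies at random and averages 5% or 10%, all non-responders, the false success chance is 0.090 or 0.180. If 80% of those lost are non-responders, it is 0.062 or 0.092. If loss is unrelated to response, it stays at 0.041.

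**If missing readings were counted as non-response over all 93.** Success then needs 46 responders and the type I error is at most 0.040. At a true rate of 60%, power is 0.985 if everyone lost is a true non-responder. If 17.2% are lost irrespective of response, the apparent rate is 0.60 × 0.828 = 49.7% and power is 0.56. A counting rule protects the error rate but does not replace the reading.

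**Complication rate.** No figure is given, because the documents state neither an expected rate nor the timing of events.

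**The case against.** The strongest reply is that the gap is narrow, and much of it stands.

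- **Events that prompt withdrawal are captured.** Surveillance covers all enrolled patients until exit. A dislodgement or embolism that leads to withdrawal precedes it and is recorded. A reader might infer that the complication rate loses the patients whose tailored system failed. The text does not support that, because only later events are lost.
- **A change of configuration is not an exit.** Lead revision or switching off a site is not among the four ways of leaving, so on the text such a patient stays on schedule. A reader might infer that stopping the tailored configuration means leaving the study. The documents do not say so, although they do not rule it out either.
- **Nothing ties withdrawal to device failure or to the 20% attrition.** That patients who do badly are the ones withdrawn is plausible but not shown. That the hardware stays in place and that the patient remains with the same hospital are also inferences, since the protocol says only that future care is unaffected.
- **The error figures depend on the analysis set.** They require an analysis of readings only, which section 5.0 neither adopts nor excludes.
- **Consent pages are not in the reviewed text.** Permission to use data after withdrawal may be given there.

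The best-interest clause protects the patient and is not itself a fault. The retention sentence asks for effort, but it keeps no data collection open once a patient has been withdrawn.

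**Conclusion.** The point holds in limited form. By its own wording the protocol ends safety surveillance "or the patient concludes his participation into the study", and investigator withdrawal is one of the ways that happens. Complications between withdrawal and day 180 therefore fall outside a rate described as covering 6 months. The loss of the month 6 echo follows from silence rather than from a stated rule.

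The direction of bias in the responder rate is upward only if withdrawal is related to poor response. The tabulated error rates, up to 0.172 with nine withdrawals, show what a few selective losses could do. They are not estimates of what will happen, and the effect disappears if loss is unrelated to response. The same gap applies to withdrawal by the patient or family where that patient would still allow data use. The change is worth making because it is cheap and prevents the missing data instead of repairing them afterwards.

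**What to change.** In Study Termination:

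1. Separate ending study procedures from ending data collection.
2. State that changing or stopping the tailored configuration does not end participation, so the month 3 and month 6 visits continue.
3. Unless the patient withdraws consent to data use, take complications and vital status from the hospital record to 180 days after implant.
4. Keep the month 6 echo for patients who agree. Otherwise use a clinical echo if one falls within 180 ± 14 days.
5. Record the reason for every withdrawal.

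In Adverse Events Recording and Reporting, change the end of surveillance to match. Report complications over all implanted patients.

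The investigator's right to withdraw a patient from study procedures is unchanged, and no clinical rule is set. The cost is protocol and consent wording and a little record review at one centre. The complication rate or the responder rate may turn out less favourable.
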